8.3.1.1.1 Events Meeting the Adverse Event Definition

Events that meet the adverse event definition:

- Any abnormal laboratory test results (hematology, clinical chemistry, or urinalysis) or other safety assessments (eg, electrocardiogram, radiological scans, vital signs measurements), including those that worsen from baseline, considered clinically significant in the medical and scientific judgment of the investigator (eg, not related to progression of underlying disease). Where applicable, clinical sequelae (not the laboratory abnormality) are to be recorded as the adverse event. In addition, laboratory or other abnormal assessments (eg, vital signs) that are associated with signs and/or symptoms must be recorded as an adverse event or serious adverse event.
- Exacerbation of a chronic or intermittent pre-existing condition including either an increase in frequency and/or intensity of the condition.
- New conditions detected or diagnosed after investigational product administration even though it may have been present before the start of the study.
- Signs, symptoms, or the clinical sequelae of a suspected drug-drug interaction.
- Signs, symptoms, or the clinical sequelae of a suspected overdose of either
 investigational product or a concomitant medication. Overdose per se will not be
 reported as an adverse event/serious adverse event unless it is an intentional
 overdose taken with possible suicidal/self-harming intent. Such overdoses should
 be reported regardless of sequelae. In case of overdosage, it is recommended
 that the subject be monitored for any signs or symptoms of adverse reactions or
 effects and appropriate symptomatic treatment be instituted immediately.
- "Lack of efficacy" or "failure of expected pharmacological action" per se will not be reported as an adverse event or serious adverse event. Such instances will be captured in the efficacy assessments. However, the signs, symptoms, and/or clinical sequelae resulting from lack of efficacy will be reported as adverse events or serious adverse events if they fulfill the definition of an adverse event or serious adverse event.

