9.5.3 Safety Endpoints

All reported adverse events will be categorized by system organ class and preferred term according to the Medical Dictionary for Regulatory Activities (latest version at the time of final analysis) dictionary and graded by CTCAE, version 4.03.

Safety analyses of the safety endpoints will be performed based on the Safety Analysis Set according to the actual treatment groups (switching group versus continued-use group). Treatment-emergent adverse events post randomization are defined as adverse events that start or worsen on or after the first dose of investigational product post randomization and prior to the EOS. The numbers and percentages of subjects reporting treatment-emergent adverse events, serious adverse events and events of interests will be tabulated by treatment group. The number and percent of subjects developing binding or neutralizing antidrug antibody (ADA) in the subset of Safety Analysis Set who have at least one ADA result post randomization will be tabulated descriptively by treatment group and by visit.

Laboratory data (hematology, serum chemistry, and urinalysis) will be converted to Système International units for reporting purposes. Absolute values and changes from week 12 for laboratory data post randomization will be summarized descriptively by treatment group and visit.

For vital signs post randomization, absolute values, and changes from week 12 will be summarized descriptively by treatment group and visit.

Physical examination values post randomization will be summarized descriptively by treatment group and by visit.

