9.5.4.2 Analyses for the Lead-in Period

All analyses for the lead-in period will be based on the Lead-in Treated Set.

Available serum concentrations over time will be summarized descriptively for each scheduled visit during the lead-in period.

Treatment-emergent adverse events during the lead-in period are defined as adverse events that start or worsen on or after the first dose of investigational product and prior to the first dose post randomization or EOS for lead-in failures.

The number and percentage of subjects reporting treatment-emergent adverse events, serious adverse events and events of interest during the lead-in period will be summarized.

The number and percentage of subjects developing binding or neutralizing ADAs during the lead-in period will be summarized.

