5.1 General

Actual Treatment Received During Lead-in Period

If a subject received any dose of ABP 501 during the Lead-in Period, the actual treatment for the subject is defined as ABP 501. Otherwise, the actual treatment for the subject is defined as Humira.

Actual Treatment Received During Post-randomization Period

For a subject randomized to switching group or continued use group and receiving all assigned treatments, the actual treatment received is defined as the switching group or the continued use group. Subjects randomized to the switching group that deviate from the switching regimen will be analyzed in a separate group and their actual treatment will be labeled "Deviated from Switching Regimen". Similarly, subjects randomized to the continued use group and deviate from this treatment regimen will be in actual treatment group labeled "Deviated from Continued use Regimen".

Baseline

Unless stated otherwise, the baseline of the study is defined as the last non-missing assessment taken prior to the first dose of investigational product (IP) a subject received (see definition of first dose date). In cases where baseline assessments are taken on the

Protocol Number: 20200497

Date: 10FEB2023 Page 13 of 36

same day as the first dose of IP, and either no times are reported or the IP and assessment times are the same, it will be assumed that these assessments are taken prior to IP being administered.

Change from Baseline

Change from baseline is defined as (value at post-baseline visit – value at baseline).

Concomitant and Prior Medication

Prior medications are defined as medications with a stop date prior to first dose of IP the subject received (see definition of first dose date). Concomitant medications are defined as any medications ongoing at the start of IP treatment for the subject or with a start date on or after the first dose date.

Developing ADA incidence

Developing antibody incidence during the Lead-in Period is defined as the number of subjects in the Lead in Treated Set (LTS) with a negative or no antibody result at baseline and a positive antibody result post-baseline (including unscheduled visits) during the Lead-in Period divided by the number of subjects in the LTS with at least one post-baseline result during the Lead-in Period.

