5.4 Safety

Adverse Events Leading to Discontinuation from IP/Study

Protocol Number: 20200497

Date: 10FEB2023 Page 19 of 36

AEs leading to discontinuation from IP/study are those with an action taken with IP indicating "drug withdrawn" or other action taken of "study discontinued".

Event of Interest (EOI)

An EOI is defined as a noteworthy event for a particular product or class of products that a sponsor may wish to monitor carefully. It could be serious or non-serious and could include events that might be potential precursors or prodromes for more serious medical conditions in susceptible individuals (Council for International Organizations of Medical Sciences [CIOMS] VI, 2005). The EOIs for this study will include:

- · Serious infections.
- malignancies,
- hypersensitivity reactions,
- demyelinating disease,
- hematological reactions,
- heart failure,
- lupus-like syndrome,
- liver enzyme elevations,
- and injection site reaction.

The detailed search strategies for the EOIs are included in Appendix A.

Treatment-emergent Adverse Event

Treatment emergent adverse events (TEAEs) during the Lead-in Period are defined as adverse events that start on or after the first dose of IP and prior to the first dose post randomization for randomized and treated subjects, or EOS for lead-in failures or for subjects who were randomized but not treated post-randomization.

TEAEs during the Post-randomization Period are defined as adverse events that start on or after the first dose of IP post-randomization and prior to the EOS.

If the adverse event starts on the same day as the first dose of IP, then the flag indicating whether the adverse event started prior to the first dose on the adverse event CRF page will be used to determine whether this is a TEAE during the Lead-in Period. For randomized and treated subjects, an adverse event that starts on the same day as the first post-randomization dose will be considered as a TEAE post-randomization.

Protocol Number: 20200497

Date: 10FEB2023 Page 20 of 36

6. Analysis Sets

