9.7.1 Adverse Events

For summary of AEs, the following summaries, (a) through (n), will be provided for the Post Randomization Period. In addition, summaries (a), (e), (f), (l) without risk difference, (m) and (n) will be provided for the Lead-in Period.

- (a) overall summary of TEAEs,
- (b) TEAEs by PT,
- (c) TEAEs by SOC and PT,
- (d) TEAEs by SOC, PT, and maximum severity grade,
- (e) treatment-emergent SAEs by PT,
- (f) treatment-emergent SAEs by SOC and PT,
- (g) grade 3 or higher TEAEs by PT,
- (h) TEAEs leading to discontinuation from IP/study by PT,
- (i) TEAEs leading to dose delayed of IP by PT,
- (j) fatal TEAEs by PT,
- (k) treatment-emergent EOIs by PT,
- (I) overall summary of treatment-emergent EOIs with risk difference,
- (m) treatment-emergent COVID-19 AEs by PT,
- (n) treatment-emergent SAEs occurring on or after the presumed start date of COVID-19 infection by PT

Counting of AEs will be by subject, and subjects will be counted only once within each SOC or PT by study period. For tables categorized by severity, subjects with multiple event PTs within a particular SOC will be counted under the category of their most severe event PT within that SOC.

AEs tabulated by preferred term will be presented in descending order of frequency of the switching group for the Post-randomization Period or the Humira group for the Leadin Period.

The risk difference and 90% CI of each treatment-emergent EOI will be calculated using Wald asymptotic confidence limits or exact confidence limits if the number of subjects for any treatment is less than 25.

A listing of treatment-emergent SAEs will be provided for the Post-randomization Period and the Lead-in Period separately.

Protocol Number: 20200497

Date: 10FEB2023 Page 32 of 36

All serious TEAEs occurring on or after the presumed start date of COVID-19 infection will be listed.

COVID-19 AEs will be flagged based on COVID-19 standardized query (SMQ) of the current MedDRA version at the time of the final analysis.

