9.7.10 Exposure to Concomitant Medication

Prior and concomitant medications will be coded using the latest available World Health Organization Drug Dictionary as of the time of the final analysis.

For the Lead-in Period, concomitant medication use by PT is summarized descriptively for the LTS and for the SAS by actual treatment group.

For the Post-randomization Period, concomitant medication use by PT is summarized descriptively by actual treatment group based on SAS.

Enter Other Analyses

Enter Analyses of Pharmacokinetic or Pharmacodynamic Endpoints

Protocol Number: 20200497

Date: 10FEB2023 Page 34 of 36

Enter Analyses of Clinical Outcome Assessments

Enter Analyses of Health Economic Endpoints

Enter Analyses of Biomarker Endpoints

10. Changes from Protocol-specified Analyses

The definition of PK Parameter Analysis Set could be too restrictive and may result in exclusion of evaluable subjects, and the protocol is not required to be amended. The PK Parameter Analysis Set was changed to consist of all randomized subjects who receive at least one IP dose post-randomization from who receive all assigned IP doses post-randomization, and who have an evaluable ABP 501 or Humira serum concentration-time profile between weeks 28 and 30. The Per-protocol PK Parameter Analysis Set was changed accordingly and consists of all subjects in the PK Parameter Analysis Set who do not have an important protocol deviation during the study that could affect the primary PK endpoints. These changes will also be documented in the Clinical Study Report.

11. Literature Citations / References

12. Prioritization of Analyses

None.

13. Data Not Covered by This Plan

None.

Protocol Number: 20200497

Date: 10FEB2023 Page 35 of 36

14. Appendices

Protocol Number: 20200497

Date: 10FEB2023 Page 36 of 36

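### SAP 5.4 drops worsening events from the treatment-emergent definitions without declaring it, and SAP 9.7.1 gives a zero-width 90% interval for any event of interest with no cases in either main group

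*SAP*

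**What the plan says.** **Treatment-emergent events.** Protocol 9.5.3 defines post-randomization events as "adverse events that start or worsen on or after the first dose of investigational product post randomization and prior to the EOS". Protocol 9.5.4.2 uses the same construction for the lead-in: "adverse events that start or worsen on or after the first dose of investigational product and prior to the first dose post randomization". The synopsis repeats the post-randomization definition. SAP 5.4 reads differently: "TEAEs during the Post-randomization Period are defined as adverse events that start on or after the first dose of IP post-randomization". Its lead-in definition also mentions only the start of an event. SAP Section 10, on changes from the protocol, deals only with the pharmacokinetic sets and opens with "The definition of PK Parameter Analysis Set could be too restrictive and may result in exclusion of evaluable subjects". The SAP version table lists no change to the treatment-emergent definition either.

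**Intervals for events of interest.** SAP 9.7.1 calculates a 90% interval for each EOI risk difference using "Wald asymptotic confidence limits or exact confidence limits if the number of subjects for any treatment is less than 25". It names no exact method. SAP 5.1 adds further actual-treatment groups: "Subjects randomized to the switching group that deviate from the switching regimen will be analyzed in a separate group". It does the same for subjects who deviate from continued use.

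**The concern.** Post-randomization treatment-emergent events and EOIs are named secondary endpoints in both documents. An analyst who follows SAP 5.4 to the letter produces a different endpoint from the one in the protocol, and Section 10 gives the reader no warning. The cases lost are lead-in events that worsen in the period where switching is compared with continued use. SAP Appendix A shows how this can reach an EOI. A serious infection there is any infection of CTCAE grade 3 or higher and/or serious. An infection that begins mildly in the lead-in and reaches grade 3 after week 12 in the same record would not enter the post-randomization count.

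The interval rule has a separate fault. Several of the nine EOIs (for example demyelinating disease or lupus-like syndrome) could have no cases in a trial of this size. For those rows the Wald formula returns an interval of no width, which claims that the difference in risk is known exactly.

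**Working it through.** **Part 1: treatment-emergent definition (no arithmetic).**

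- Protocol, post-randomization: the event starts or worsens on or after the first post-randomization dose and before end of study. SAP: the event starts in that window.
- Protocol, lead-in: starts or worsens. SAP: starts.
- Protocol 8.3.1.1.1 already makes this an adverse event: "Exacerbation of a chronic or intermittent pre-existing condition including either an increase in frequency and/or intensity of the condition". If the site opens a new record for an exacerbation, that record has its own start date and SAP 5.4 captures it.
- What remains is mainly one continuing record that begins in the lead-in and increases in grade after the first post-randomization dose. Neither document gives a rate for this or says whether the CRF dates a grade increase, so no number can be attached.

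**Part 2: EOI intervals.**

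Inputs: 342 randomized 1:1 (SAP 3.2), hence 342/2 = 171 per group. The plan's figures agree: 414 enrolled × (1 − 0.17) = 343.6, or approximately 342. The level is 90%, so z = 1.645. The plan gives no EOI rates, so every rate below is assumed.

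*Which limits apply.* SAP 9.1 takes percentages over the number of subjects in the analysis set for each treatment group. With the same meaning in 9.7.1, the threshold of 25 refers to group size. At or near 171 per group the main comparison never reaches it, so Wald limits always apply.

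*Wald:* difference ± z·√[p₁(1−p₁)/n + p₂(1−p₂)/n].
- 0 v 0: the standard error is 0, so the interval is (0, 0).
- 1 v 0: p₁ = 1/171 = 0.585%, standard error 0.583%, giving 0.585 ± 0.959 = (−0.37, 1.54).

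*Miettinen-Nurminen:* the score statistic with restricted maximum-likelihood risks and the factor N/(N−1), N = 342. For 0 v 0 the restricted risks at difference d are d and 0. The limit then solves d²/{[d(1−d)/n]·N/(N−1)} = z². This gives d = k/(n+k), with k = 2.7055 × 342/341 = 2.7135. So d = 2.7135/173.7135 = 1.56%.

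90% limits in percentage points, 171 per group:

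| Cases | Wald | Miettinen-Nurminen |
|---|---|---|
| 0 v 0 | (0, 0) | (−1.56, 1.56) |
| 1 v 0 | (−0.37, 1.54) | (−0.98, 2.58) |
| 2 v 0 | (−0.18, 2.52) | (−0.40, 3.48) |
| 10 v 8 | (−2.80, 5.14) | (−2.97, 5.42) |

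With about 145 per group (15% fewer), 0 v 0 is (0, 0) v ±1.84.

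*Chance of a 0 v 0 row.* With common risk r it is (1−r)^342: 71% at 0.1%, 50% at 0.2%, 18% at 0.5% and 3% at 1%.

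*Coverage of the nominal 90% interval, by enumerating two binomials of size 171.*

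| True risks | Wald | Miettinen-Nurminen |
|---|---|---|
| 0.55% v 0.05% | 61% | 98.5% |
| 1.1% v 0.1% | 84% | 94% |
| 1% v 0.5% | 80% | 92% |
| 2% v 1% | 90% | 90% |
| equal: 0.1%, 0.5%, 1%, 2%, 5% | 99.9%, 95.2%, 89.3%, 87.5%, 89.9% | the same |

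The first row shows the mechanism. P(0 v 0) = 0.9945^171 × 0.9995^171 = 0.389 × 0.918 = 0.357, and on each such occasion the Wald interval (0, 0) misses the true difference of 0.5 points. That accounts for about 36 of the 39 points of lost coverage.

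*Secondary point.* If exact limits were ever used, the method would matter. For 0 v 0 an exact unconditional interval on the score statistic is ±1.74 points (1 − 0.05^(1/171) = 1.74%). One on the raw difference is wider.

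**The case against.** Safety is assessed descriptively (Protocol 2.1). No margin or hypothesis is attached to the EOI intervals, and the counts should stand in the same summary, so a reader can see that (0, 0) means no events. Wald and Miettinen-Nurminen coverage agree at every equal risk checked; they separate only for rare, unequal risks, and the documents give no rates. On the definition, the rule is the same in both groups, and a lead-in event that later worsens still appears in the lead-in overall summary. All of this stands and keeps the point minor. It does not make a zero-width interval right, and it does not declare the departure from the protocol.

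A reader might infer something stronger from the threshold of 25, in either of two ways:

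- It might be taken to count subjects with the event. The only support is "Counting of AEs will be by subject, and subjects will be counted only once within each SOC or PT by study period", which prevents double counting and does not redefine the number of subjects for a treatment.
- A small group of deviating subjects under SAP 5.1 might be taken as one of the treatments, moving the main comparison to exact limits. The wording does not rule this out. But a risk difference compares two groups, and it is strained to let a third choose the method.

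Only under one of these readings, and with the raw-difference exact statistic, does a 0 v 0 row reach ±9.16 points. The documents choose neither, so that width should not be presented as what the plan will produce.

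**Conclusion.** Both faults hold as stated, at minor severity. The omission of worsening from SAP 5.4 is a plain, undeclared difference from the protocol; its size is unknown and is narrowed by Protocol 8.3.1.1.1. On the natural group-size reading, SAP 9.7.1 gives a 90% interval of (0, 0) for any EOI with no cases in either main group, against about ±1.56 points. It also undercovers when risks are rare and unequal. These figures assume 171 per group, which is the planned randomized size; the main safety groups may be smaller. The coverage figures also rest on assumed event rates. That the exact method is unnamed, and that small deviating groups might trigger it, is a secondary lack of clarity.

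The documents do not support reading this as a threat to the interchangeability conclusion. That rests on the 90% intervals for AUCtau and Cmax, which neither fault touches.

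**What to change.** - **SAP 5.4:** restore the worsening clause in both period definitions. If the CRF does not date a grade increase within one record, say so and declare the change in SAP Section 10. Cost: two words in each definition, or one declared sentence. A continuing event that worsens would then count in both periods, which fits the SAP's counting of subjects by study period.
- **SAP 9.7.1:** use Miettinen-Nurminen score limits for every EOI risk difference that is reported, including any that involves a group deviating from its regimen, and delete the threshold of 25. This removes the zero-width rows, the question of what is counted and the unnamed exact method. Cost: one sentence. The limits are somewhat wider (10 v 8: about 8.4 points in total against 7.9). They do not guarantee 90% coverage: at a common 2% risk they reach 87.5%, the same as Wald.

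Neither change alters the sample size or the primary analysis. The interval change needs no new data, and the definition change needs none if the CRF dates grade increases.

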9.7.2 Laboratory Test Results

Laboratory data (hematology, serum chemistry, and urinalysis) will be converted to Système International units for reporting and processing purposes.

For the Post-randomization Period, absolute values and changes from baseline by visit will be presented descriptively. In addition, shift tables of the worst post-randomization laboratory toxicity based on CTCAE grading relative to randomization at week 12 will be presented. The shift tables will take into account all post-randomization (schedule and unscheduled) laboratory results in the determination of the worst post-randomization laboratory toxicity. Furthermore, subject incidence tables of grade ≥ 3 laboratory toxicities will be provided. Standard ranges will be used for the laboratory analysis.

For the Lead-in Period, absolute values and changes from baseline by visit will be presented descriptively.

Lab assessments will be grouped for summary as follows:

Hematology: white blood cell parameters: white blood cell count and differential,

Hematology: red blood cell parameters: hemoglobin, hematocrit, red blood cell count, absolute neutrophil count,

Hematology: other parameters: platelets,

Serum chemistry: hepatobiliary parameters: alanine aminotranferase (ALT), aspartate aminotransferase (AST), total bilirubin, alkaline phosphatase, gamma glutamyl transferase,

Serum chemistry: general chemistry: sodium, potassium, albumin, total protein, glucose (random),

Serum chemistry: renal function tests: blood urea nitrogen, creatinine,

Urinalysis: pH, specific gravity, glucose, bilirubin, blood, and protein.

9.7.3 Vital Signs

Observed and change from baseline for each vital sign parameter will be summarized descriptively by visit for the Post-randomization Period.

Protocol Number: 20200497

Date: 10FEB2023 Page 33 of 36

